7.7.1. Definition of Childbearing Potential

For the purposes of this study, a female subject of childbearing potential is a pubertal female regardless of whether or not she has had a menses (premenarchal, Tanner Stage 3). This also includes a female subject who has not had any of the following conditions or procedures considered very rare in this age group: hysterectomy, bilateral oophorectomy, or medically documented ovarian failure.

7.7.2. Contraceptive Requirements

Male study subjects and female study subjects of childbearing potential who are not heterosexually active should have periodic confirmation of continued abstinence from heterosexual intercourse and regular pregnancy testing while taking tenofovir DF. Female study subjects of childbearing potential who have been identified during the study as choosing to become sexually active should be counseled appropriately on the protocol-recommended method(s) for avoiding pregnancy in case the subject chooses to continue with heterosexual intercourse.

Male and female subjects of childbearing potential who engage in heterosexual intercourse must either agree to use protocol-recommended method(s) of contraception or agree to abstain from heterosexual intercourse from the Screening/Enrollment Visit throughout the study period and for 30 days following the last dose of tenofovir DF. The investigator should identify those subjects at risk for becoming sexually active and provide counsel appropriately on the protocol-recommended method(s) for avoiding pregnancy during the trial. These methods are recommended due to the low failure rate (i.e., less than 1% per year). See [Table 7-1](#) for the protocol-recommended methods.

Female subjects of childbearing potential must have a negative serum pregnancy test at Screening and Baseline (Day 1) prior to receiving the first dose of study drug. Lactating females will not be enrolled in this study.

Table 7-1. Protocol-Recommended Contraceptive Methods

Single Methods	Combination Methods

Intra-uterine devices (IUDs)
 
 • Copper T 380A IUD • LNg 20 IUD 
Progesterone
 
 • Implant 	
Estrogen and Progesterone
 
 • Oral contraceptives plus barrier • Transdermal patch plus barrier • Vaginal ring plus barrier 
Progesterone
 
 • Injection plus barrier 
Barrier methods
 
 • Diaphragm • Cervical cap • Male condom

Other contraceptive methods may be acceptable after discussion with the Medical Monitor.

7.7.3. Procedures to be Followed in the Event of Pregnancy

The investigator must report all pregnancies to Gilead Sciences DSPH via the CRO within 24 hours of becoming aware of the pregnancy. Any pregnancies that occur within 30 days of last investigational medicinal product dose should also be reported. The subject must be instructed to discontinue all investigational medicinal products and inform the investigator **immediately** if she becomes pregnant or suspects that she is pregnant during the study.

The investigator should counsel the subject regarding the possible effects of prior investigational medicinal product exposure on the fetus and the need to inform the study site of the outcome of the pregnancy.

The pregnancy itself is not considered an AE nor is an induced elective abortion to terminate a pregnancy without medical reasons.

However, an induced therapeutic abortion to terminate any pregnancy due to complications or other medical reasons will be recorded as an AE or an SAE. The underlying medical reason for this procedure should be recorded as the adverse event term.

A spontaneous abortion is always considered to be an SAE and will be reported as described in the Adverse and Serious Adverse Events section. Furthermore, any SAE occurring as an adverse pregnancy outcome post-study must be reported to Gilead Sciences DSPH or the CRO.

All pregnancies of female study subjects that occur during the study should be reported using the Pregnancy Report CRF page and the Gilead DSPH Pregnancy form and Pregnancy Outcome form. Monitoring of the subject should continue until the conclusion of the pregnancy. If the end of the pregnancy occurs after the study has been completed, the outcome should be reported directly to Gilead Sciences DSPH, [contact] or email [contact].

8. STATISTICAL CONSIDERATIONS

8.1. Analysis Objectives

The primary objective of this study is:

- To evaluate the antiviral efficacy of tenofovir DF versus placebo in pediatric patients (aged 2 to <12 years, at the time of enrollment) with chronic hepatitis B infection

The key secondary objective is:

- To evaluate the proportion of subjects with HBeAg seroconversion at Week 48 (in subjects with baseline HBeAg sero-positivity).

Secondary objectives are:

- To characterize the safety and tolerability profile of tenofovir DF in pediatric patients (aged 2 to <12 years, at the time of enrollment) with chronic hepatitis B infection
- To evaluate the biochemical and serological responses to tenofovir DF versus placebo
- To evaluate the incidence of potential resistance mutations to tenofovir DF in the hepatitis B virus polymerase /reverse transcriptase (pol/RT)
- To assess the pharmacokinetics of tenofovir in subjects receiving the tablet formulation and those receiving the oral powder formulation.

8.2. Primary Endpoint

The primary efficacy endpoint is the proportion of subjects with serum HBV DNA < 400 copies/mL (69 IU/mL) at Week 48. A missing = failure approach will be employed for handling missing data.

8.3. Key Secondary Endpoint

The key secondary endpoint is the proportion of subjects with HBeAg seroconversion at Week 48 (in subjects with baseline HBeAg sero-positivity). A missing = failure approach will be employed for handling missing data.

8.4. Secondary Endpoints

For Week 48, secondary endpoints to be evaluated in all subjects include:

- proportion of subjects with normal ALT and normalization of ALT
- composite endpoint of proportion of subjects with HBV DNA < 400 copies/mL and normal ALT

- proportion of subjects with HBV DNA < 169 copies/mL (29 IU/mL)
- proportions of subjects with HBsAg loss and seroconversion
- sequence changes from baseline within the HBV polymerase for subjects who were viremic (HBV DNA \geq 400 copies/mL [69 IU/mL]) at Weeks 48, 96, 144, 192 or Early Discontinuation; including subjects with confirmed virologic breakthrough
- cumulative incidence of at least a 4% decrease from baseline in bone mineral density of lumbar spine
- percent change from baseline in bone mineral density of lumbar spine

8.5. Other Endpoints of Interest

For Week 48, secondary endpoints to be evaluated in HBeAg-positive subjects include:

- proportions of subjects with HBeAg loss
- composite endpoint of proportion of subjects with HBV DNA < 400 copies/mL (69 IU/mL), normal ALT and HBeAg loss
- composite endpoint of proportion of subjects with HBV DNA < 400 copies/mL (69 IU/mL), normal ALT, and HBeAg seroconversion.

For Week 48, secondary endpoints to be evaluated in subjects with abnormal ALT at baseline include:

- proportion of subjects with normalized ALT
- composite endpoint of proportion of subjects with HBV DNA < 400 copies/mL (69 IU/mL) and normalized ALT

For Week 48, secondary endpoints to be evaluated in HBeAg-positive subjects with abnormal ALT at baseline include:

- composite endpoint of proportion of subjects with HBV DNA < 400 copies/mL (69 IU/mL), normalized ALT and HBeAg loss
- composite endpoint of proportion of subjects with HBV DNA < 400 copies/mL (69 IU/mL), normalized ALT, and HBeAg seroconversion.

Secondary endpoints to be evaluated in PK substudy populations on tablet formulation and oral powder are the plasma pharmacokinetic parameters including CL/F, C_{max} , T_{max} , C_{last} , T_{last} , C_{tau} , λ_z , $T_{1/2}$, AUC_{0-last} , AUC_{tau} .

For all categorical secondary endpoints, missing data will be handled using a missing = failure approach.

All endpoints at Week 48 will also be analyzed at Weeks 144 and 192.

8.6. Methods of Analysis

All summary tables for efficacy endpoints will present data by treatment group (TDF or Placebo) and overall.

8.6.1. Analysis Sets

8.6.1.1. Efficacy

The primary analysis set for efficacy analyses will be defined as all randomized subjects who received at least one dose of study drug (referred to hereafter as the full analysis set [FAS]). Subjects who withdraw after randomization prior to receiving study drug will be excluded from the FAS. Subjects discontinuing randomized therapy prior to Week 48 will be handled using a missing = failure approach, as noted in Sections 8.2 and 8.3, for the purpose of the primary and key secondary efficacy analyses. Subjects will be analyzed according to the randomized treatment assignment.

8.6.1.2. Safety

The primary analysis set for safety analyses will include all randomized subjects who received at least one dose of study drug. All data collected during the course of the study (on treatment and during treatment-free follow up) will be included in the safety summaries. Subjects will be analyzed according to the treatment actually received.

8.6.1.3. Pharmacokinetics

The PK analysis set will include all subjects who have evaluable pharmacokinetic data.

8.6.2. Data Handling Conventions

Missing data can have an impact upon the interpretation of the trial data. In general, values for missing data will not be imputed.

For the primary endpoint and categorical secondary efficacy endpoints, missing data will be considered a failure, as noted in Sections 8.2 and 8.3.

Sensitivity analyses will be performed if warranted.

8.6.3. Multiplicity Adjustments

A sequential gatekeeping procedure will be employed. The key secondary endpoint will only be tested at a 0.05 level if the primary endpoint is statistically significant at a 0.05 level.

8.6.4. Interim Analysis

An external independent multidisciplinary Data Monitoring Committee (DMC) will review the progress and safety of this study approximately every 24 weeks after the first subject is randomized. During the open-label duration of the study, the DMC will convene approximately every 52 weeks. See Section 8.12 for discussion of Data Monitoring Committee interim analyses.

No efficacy analyses are planned prior to the primary efficacy analysis, which will be conducted at the end of double-blind treatment, after the last randomized subject reaches Week 48.

8.7. Demographic Data and Baseline Characteristics

Demographic and baseline measurements will be summarized using standard descriptive methods by treatment group, and overall.

Demographic summaries will include gender, ethnic origin (with Asian-Chinese, Asian-Indian, Asian-Other all combined to Asian), racial minority, age, and geographical location of study site [North America/Europe, and Asia]).

Baseline data will include a summary of body weight, height, body mass index, \log_{10} (HBV DNA) level, HBV serology, ALT/AST values, previous nucleoside and interferon exposure, genotype, bone mineral density (via DEXA scan), and serum bone biochemical markers.

8.8. Efficacy Analysis

8.8.1. Primary Analysis

The primary efficacy analysis will be conducted at the end of double-blind treatment, after the last randomized subject reaches Week 48. The analysis will evaluate the difference between treatment groups in the proportion of subjects achieving the primary endpoint, using a two-sided Fisher's exact test.

8.8.2. Key Secondary Analysis

The key secondary efficacy analysis will be conducted at the end of double-blind treatment, after the last randomized subject reaches Week 48. The analysis will evaluate the difference between treatment groups in the proportion of subjects achieving the key secondary efficacy endpoint, using a two-sided Fisher's exact test.

8.8.3. Secondary Analyses

Continuous secondary efficacy endpoints will be summarized using conventional descriptive statistics (n, mean, standard deviation, median, Q1, Q3, minimum and maximum) by treatment group, and a Wilcoxon rank sum test may be used to compare treatment groups. Categorical secondary efficacy endpoints will be summarized by number and percentage of subjects that meet the endpoint, and a two-sided Fisher's exact test may be used to compare treatment groups. For analyses of categorical secondary efficacy endpoints, missing data will be handled using a missing = failure approach.

Subgroup analyses of efficacy endpoints may include analyses by geographical location of study site (North America/Europe, and Asia), and also by presence/absence of prior oral anti-HBV treatment.

Efficacy analyses of all subjects continuing on open-label tenofovir DF will also be performed after the last randomized subject reaches Weeks 144 and 192.

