3.3. Strata and Covariates

Randomization was stratified by age (2 to <6 and 6 to <12 years at the time of enrollment) and geographical location of study site (North America/Europe, and Asia). For all stratified analyses, age at baseline (<6 and ≥ 6 years) and geographical location of study site (North America/Europe, and Asia) will be used. If the number of subjects in a particular stratum is too small, this stratum may be combined with other strata for analysis. If there are discrepancies in stratification factor values between the IWRS and the clinical database at screening or baseline, the values recorded in the clinical database at baseline (or screening, if baseline is missing) will be used for stratified analyses.

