6.2.2. Analysis Methods for Secondary Efficacy Endpoints

The analyses for the secondary efficacy endpoints will be conducted using the FAS, unless otherwise specified. Specifically, for endpoints including ALT normalization, the subset of subjects in the FAS with baseline abnormal ALT will be used, for HBeAg loss and HBeAg seroconversion, the Serologically Evaluable FAS for HBeAg Loss/Seroconversion will be used, and for HBsAg loss and HBsAg seroconversion, the Serologically Evaluable FAS for HBsAg Loss/Seroconversion will be used.

Normal ALT and normalization of ALT analyses will each be repeated twice, once using the central laboratory ULN and once using the AASLD ULN.

Categorical secondary efficacy endpoints will be summarized by number and percentage of subjects that meet the endpoint, and a two-sided CMH test stratified by age at baseline (< 6 vs. ≥6 years) and region (North America/Europe vs Asia) will be performed. Analyses will also be repeated using the M = F and the M = E approach.

Incidence of drug resistant mutations will be reported in a separate virology report. The virology team may be unblinded in advance to identify which samples are required for analysis.

In addition, log₁₀ HBV DNA (IU/mL), ALT (U/L) and log₁₀ HBsAg (IU/mL), and corresponding change from baseline values, will be summarized by visit using observed data. P-values will be calculated using the two-sided Wilcoxon rank-sum test.

The proportion of subjects with HBV DNA < 69 IU/mL [400 copies/mL] using both the M = F and M = E approach, proportion of subjects with HBeAg seroconversion using the M=F approach only, proportion of subjects with normalized ALT by central lab and AASLD normal ranges, mean log₁₀ HBV DNA (IU/mL), mean log₁₀ HBsAg (IU/mL), and mean ALT (U/L) will be plotted with 95% CIs over time. Supportive listings for the analyses of the secondary endpoints will also be generated.

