6.4. Changes From Protocol-Specified Efficacy Analyses

The protocol specifies that the analysis of the primary efficacy endpoint will evaluate the difference between the TDF and placebo treatment groups using a two-sided Fisher's exact test. This has been modified to a CMH test, controlling for the age group at baseline and region, in order to account for the stratified randomization used in the study. The age group at baseline was specified as <6 vs. ≥6 years, compared to the randomization strata age group of 2 to <6 and 6 to <12 years, as some subjects were age 12 by baseline. This change was also made for the analyses of the secondary endpoints. The two-sided Fisher's exact test will still be performed as a secondary analysis of the primary endpoint.

The PP Analysis Set, Serologically Evaluable FAS for HBeAg Loss/Seroconversion, and Serologically Evaluable FAS for HBsAg Loss/Seroconversion, was not defined in the protocol, but was added in the SAP.

For HBV DNA analyses, the default will be to report measurements in IU/mL, which is the current clinically accepted way to describe this parameter, instead of copies/mL.

For ALT normalized and normal analyses, both the AASLD and central lab normal ranges will be used.

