7.4. Renal Safety Analyses

7.4.1. Estimated Glomerular Filtration Rate (eGFR)

Glomerular filtration rate (estimated creatinine clearance) will be calculated using the Schwartz formula for subjects ages 2 to <18 as follows:

$$\text{Schwartz formula (mL/min/1.73 m}^2\text{)} = k \times L/\text{Scr}$$

k is a proportionality constant,

k = 0.55 for pediatric males and females ≥ 2 years to < 12 years;

k = 0.55 for adolescent females ≥ 12-18 years old; and

k = 0.70 for adolescent males ≥ 12-18 years old

L is height in centimeters (cm); and

Scr is serum creatinine (mg/dL).

Summaries of eGFR and change from baseline in eGFR at baseline and at each postbaseline visit will be provided during the double-blind phase. Comparison of change from baseline in eGFR between the 2 treatment groups will be performed using the two-sided Wilcoxon rank-sum test. Median (Q1, Q3) change from baseline in eGFR over time will be plotted.

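### Changes from baseline in HBV DNA, ALT, HBsAg and eGFR are compared by a valid but inefficient Wilcoxon test, without baseline as a covariate or the randomisation strata

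*Protocol*

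**What the plan says.** - **Protocol 8.8.3** is permissive and names no specific measure: "and a Wilcoxon rank sum test may be used to compare treatment groups".
- **SAP 6.2.2** is the operative text. It adds log10 HBV DNA, ALT in U/L and log10 HBsAg, "and corresponding change from baseline values, will be summarized by visit using observed data". The test follows: "P-values will be calculated using the two-sided Wilcoxon rank-sum test". No covariate or stratum is named.
- **SAP 7.4.1** treats renal function the same way: "Comparison of change from baseline in eGFR between the 2 treatment groups will be performed using the two-sided Wilcoxon rank-sum test".
- **SAP 6.2.2** handles the categorical endpoints differently: "Categorical secondary efficacy endpoints will be summarized by number and percentage of subjects that meet the endpoint, and a two-sided CMH test stratified by age" and region.
- **SAP 6.4** explains the move from Fisher's exact test to CMH for the primary endpoint: "in order to account for the stratified randomization used in the study". It adds: "This change was also made for the analyses of the secondary endpoints".
- **SAP 3.3** gives the strata, "Randomization was stratified by age (2 to <6 and 6 to <12 years at the time of enrollment) and geographical location of study site", and lets a stratum that is too small be combined with others.
- **SAP 7.3.1** uses a baseline-adjusted rank ANCOVA, but only for shifts in BMD Z-score category.

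**The concern.** The reason given for stratifying the categorical endpoints is how subjects were randomised. It applies equally to continuous outcomes analysed in the same subjects, and the SAP does not say why these are treated differently.

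The change score subtracts the whole baseline value. When the correlation between baseline and follow-up is below 1, that over-corrects, and part of the spread in the change scores is baseline noise that a covariate would remove. ALT is the clearest case: Protocol 4.2 requires at least 1.5 × ULN at entry with no upper limit, so baseline values may spread widely.

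What is at stake is precision. SAP 1.3 reports that enrolment stopped at 90 randomised and 89 treated, which leaves about 29 or 30 placebo subjects. In a comparison of that size, a moderate difference in ALT, HBsAg or eGFR could be missed although the data needed to sharpen the test have already been collected.

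**Working it through.** **1. The plan's own figure.** The only stated power is for the binary primary endpoint: at least 85% with 67 versus 33 subjects, 21% versus 1%, two-sided Fisher's exact test at 0.05. Exact enumeration gives 88.3%, so the statement is reproduced. No SD, effect size, correlation or power is stated for the continuous measures. Everything below is therefore a range over assumptions.

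**2. Algebra.** Take equal SD *s* at baseline and follow-up, and correlation *r*.

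- Variance of the change score: 2*s*²(1 − *r*)
- Residual variance with baseline as covariate: *s*²(1 − *r*²)
- Ratio: (1 − *r*²) / [2(1 − *r*)] = (1 + *r*)/2

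| *r* | 2(1 − *r*) | 1 − *r*² | ratio |
|---|---|---|---|
| 0.3 | 1.40 | 0.91 | 0.65 |
| 0.5 | 1.00 | 0.75 | 0.75 |
| 0.7 | 0.60 | 0.51 | 0.85 |
| 0.9 | 0.20 | 0.19 | 0.95 |

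**3. Simulated power at a fixed moderate effect.** Inputs: 60 versus 29 (89 treated at 2:1 is 59.3 to 29.7; the exact split is assumed), bivariate normal data, true effect 0.6 SD, strata carrying no effect, two-sided 0.05. The Wilcoxon test on change is compared with a regression of the ranks of change on treatment, baseline rank and strata.

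| *r* | Wilcoxon on change | Rank ANCOVA | gain (points) |
|---|---|---|---|
| 0.3 | 59% | 73% | 14 |
| 0.5 | 73% | 81% | 8 |
| 0.7 | 91% | 94% | 3 |
| 0.9 | about 100% | about 100% | 0 |

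With no true effect, both methods reject in about 5% of trials. Repeat runs agree to within about 2 points.

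**4. Is the zero gain at *r* = 0.9 only a ceiling effect?** To check, the effect was reset at each *r* so that a t-test on change has 80% power: *d* = (1.96 + 0.84) × √[2(1 − *r*)] × √(1/60 + 1/30), with 60 versus 30 subjects.

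| *r* | *d* (SD) | Wilcoxon | Rank ANCOVA | ANCOVA |
|---|---|---|---|---|
| 0.3 | 0.741 | 77% | 91% | 93% |
| 0.5 | 0.626 | 78% | 86% | 89% |
| 0.7 | 0.485 | 77% | 83% | 85% |
| 0.9 | 0.280 | 78% | 79% | 82% |

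So the gain does shrink towards nothing as *r* rises.

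**5. Stratification on its own.** In the step 4 design, a stratified Wilcoxon (van Elteren) test gains nothing when the strata do not predict change (a loss of 0 to 1 point). With an assumed stratum effect of 0.5 SD it gains 0, 1, 3 and 10 points at *r* = 0.3, 0.5, 0.7 and 0.9.

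**6. Large effects.** At *r* = 0.5 with a 0.5 SD stratum effect, power at 1 SD is 98.6% for Wilcoxon and 99.9% for ANCOVA. At 1.5 SD and above every method reaches about 100%.

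**7. Skewed data.** ALT is tested untransformed. With assumed lognormal values (log SD 0.7, effect 0.6 SD on the log scale), Wilcoxon gives 48%, 59% and 78% at *r* = 0.3, 0.5 and 0.7, and rank ANCOVA 67%, 76% and 90%: gains of 19, 17 and 12 points.

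**The case against.** The strongest reply is that nothing here is wrong, only less efficient than it might be, and that no main conclusion depends on it. Most of that stands.

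- **Validity.** Type I error is nominal. Chance baseline imbalance adds variance in a randomised comparison, not bias.
- **Status.** Changes in HBV DNA, ALT and HBsAg are not among the endpoints listed in Protocol 8.4 and 8.5 or SAP 6.2.1; SAP 6.2.2 brings them in as additional by-visit summaries. Change in eGFR is a safety summary. The gatekeeping in SAP 3.5 covers only HBV DNA suppression and HBeAg seroconversion.
- **HBV DNA.** SAP 1.3 cites 86.5% suppression at Week 48 on TDF in adolescents, and Protocol 8.11 cites 0% response on placebo. An effect of that order leaves little to gain.
- **Method.** The rank ANCOVA in SAP 7.3.1 adjusts for baseline status only, on a categorical shift. Extending it to continuous changes with strata has to be written out, and with about 29 placebo subjects over four strata some pooling may be needed.

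Two stronger readings are tempting, and the documents support neither. A reader might infer from SAP 6.4 that all secondary analyses were promised a stratified test and that the continuous ones break the promise. The change described there is Fisher to CMH, which can only concern categorical endpoints, and SAP 6.2.2 carries it out for those. A reader might also say that the test ignores baseline. It does not, since a change score subtracts it; what is missing is baseline as a covariate.

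What the reply does not remove is that the information is already collected, the stated reason for stratifying applies here too, and the loss at moderate effects can exceed 10 points.

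**Conclusion.** The point holds as a matter of efficiency and evenness of approach. For change in log10 HBV DNA, ALT, log10 HBsAg and eGFR, the SAP uses a valid two-sample test that forgoes available precision, while its categorical secondary analyses use the strata.

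On normal data with a 0.6 SD effect and about 60 versus 29 subjects, the forgone power is about 14, 8 and 3 points at *r* = 0.3, 0.5 and 0.7, and nil at 0.9. It is larger if the data are skewed, as is plausible for ALT, and small at effects of 1 SD or more unless *r* is low or the data are skewed. Nearly all of the gain comes from the baseline value; the strata add to it only if they predict change.

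The correlations, effect size, distributions and exact split are assumptions, because the documents give none for these measures. The primary and key secondary conclusions are unaffected. The practical benefit is for ALT, HBsAg and eGFR.

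**What to change.** Before unblinding:

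1. In SAP 6.2.2 and 7.4.1, test change from baseline with a rank ANCOVA (or ANCOVA) that includes the baseline value, age group (<6, ≥6 years) and region. Choose one of the two in advance. For untransformed ALT the rank version is the safer choice.
2. State how small strata will be pooled, following SAP 3.3.
3. Keep the two-sided Wilcoxon test as a supportive analysis.
4. Add a sentence to SAP 6.4 saying that the change from Fisher to CMH covers categorical endpoints only, and record the new test for continuous changes as a separate change.

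Protocol 8.8.3 is permissive and needs no amendment. The cost is SAP wording and a few lines of code; no new data are needed.
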